8.3.1.4 Supplementary Analysis

8.3.1.4.1 Alternative Estimand using Hypothetical Strategy

An alternative estimand will be defined similarly to the primary estimand with the exception that ICE will be addressed using the hypothetical strategy. In the hypothetical strategy, observed values after ICE will be set to missing to provide a conservative and robust test of non-inferiority for the primary endpoint. Supplementary analysis of this alternative estimand will be performed similarly to the primary analysis as specified in 8.3.1.3. Additional details are presented in [Appendix](#).

8.3.1.5 Subgroup Analysis

Subgroup analyses of the primary efficacy endpoint will be performed for each of the following subgroups:

- Age at screening (<18; ≥18 years)
- ppFEV₁ at baseline (<70; ≥70 percentage points)
- SwCl at baseline (<30; ≥30 mmol/L)
- Sex (male; female)
- Geographic region (North America [including United States]; Rest of the World [including Europe, Israel, Australia, and New Zealand])

The MMRM used for the primary analysis of the primary estimand (8.3.1.3) will be used for the subgroup analyses, where the same model will be applied to each category of the subgroup. Note that for the subgroup analysis based on age, the term age at screening (<18 versus ≥18 years of age) will be removed from the MMRM. The adjusted means with 2-sided 95% CIs will be provided. Furthermore, the estimated treatment difference through Week 24 (estimated by averaging Weeks 16 and 24) in different categories within a subgroup will also be presented in a forest plot. Note: The results from the subgroup analyses should be interpreted with caution in the cases where sample sizes are small.

8.3.2 Analysis of Key Secondary Efficacy Variables

The tests for absolute change from baseline in SwCl through Week 24 (continuous variable) based on the FAS and the proportion of subjects with SwCl <60 mmol/L and SwCl <30 mmol/L through Week 24 based on the PFAS will be subject to multiplicity control. Note that the within-study analyses of the proportion of subjects with SwCl <60 mmol/L through Week 24 and the proportion of subjects with SwCl <30 mmol/L through Week 24 based on the FAS are Other Secondary Endpoints and are not subject to multiplicity control; analyses of these endpoints are described in 8.3.3.

8.3.2.1 Definition of Variables

Sweat chloride (SwCl): The SwCl value at a given visit will be calculated as the mean of the non-missing sweat chloride measurements obtained on the left and right arms at that visit. If one of the two arm measurements at a time point is missing, the other will be used as the mean. A volume ≥15 µL is required for an accurate determination of sweat chloride. Any results reported as having volume <15 µL will be considered missing. Any sweat chloride values reported as

>160 mmol/L will be considered missing. Any sweat chloride values reported as <10 mmol/L will be imputed as 10 mmol/L.

8.3.2.2 Analysis Method

Absolute change from baseline in SwCl through Week 24:

The estimand for the absolute change from baseline (after ELX/TEZ/IVA run-in) in SwCl through Week 24 is defined as the following:

- Treatment: VNZ/TEZ/D-IVA versus ELX/TEZ/IVA
- Population: Study population represented by inclusion and exclusion criteria
- Variable: Absolute change from baseline in SwCl through Week 24 (estimated by averaging Weeks 16 and 24)
- Handling of ICE: Same as the primary estimand (8.3.1.2)
- Population level summary: Difference in variable means between VNZ/TEZ/D-IVA and ELX/TEZ/IVA groups

The analysis of absolute change from baseline in SwCl through Week 24 will be based on an MMRM similar to the primary analysis of the primary estimand (8.3.1.3), with absolute change from baseline in SwCl at Day 15, Week 4, Week 16, and Week 24 as the dependent variable. The estimated treatment difference through Week 24 (estimated by averaging Weeks 16 and 24) will be presented along with the 2-sided 95% CI and *P* value. The estimated within-group change from baseline and treatment difference at each post-baseline visit, obtained from the model, will be provided. The estimated within-group change and its SE at each post-baseline visit will also be plotted by treatment group.

Proportion of subjects with SwCl <60 mmol/L through Week 24 (pooled with data from Study 103):

The estimand for the proportion of subjects with SwCl <60 mmol/L through Week 24 is defined as the following:

- Treatment: VNZ/TEZ/D-IVA versus ELX/TEZ/IVA
- Population: Pooled study population represented by inclusion and exclusion criteria
- Variable: Response defined as SwCl <60 mmol/L through Week 24 (estimated by averaging Weeks 16 and 24)
- Handling of ICE: Same as the primary estimand (8.3.1.2)
- Population level summary: Odds ratio comparing the response rates in VNZ/TEZ/D-IVA and ELX/TEZ/IVA groups

The response corresponding to SwCl <60 mmol/L at each visit through Week 24 in the PFAS will be analyzed using a generalized estimating equations (GEE) model. The model will include fixed categorical effects for treatment, age at screening (<18 versus ≥18 years of age), genotype group (F/MF, F/F, F/G, F/RF, TCR/non-F), visit, and treatment-by-visit interaction, with baseline ppFEV₁ and baseline SwCl as continuous covariates. A logit link function and an unstructured working correlation matrix will be used in the GEE model. If the model estimation

does not converge, genotype group will be considered with three levels (F/MF, F/F and Other) or removed from the model, and if non-convergence persists, an alternative covariance structure like compound symmetry will be used. The estimated odds ratio through Week 24 (estimated by averaging Weeks 16 and 24) along with the 2-sided 95% CI and *P* value will be presented. The estimates for each visit through Week 24 will also be presented. The number and proportion of subjects with SwCl <60 mmol/L at each post-baseline visit through Week 24 will be descriptively summarized by treatment group.

Proportion of subjects with SwCl <30 mmol/L through Week 24 (pooled with data from Study 103):

The estimand and analysis will be similar to that for the pooled analysis of proportion of subjects with SwCl <60 mmol/L through Week 24.

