8.3.1.3 Primary Analysis

The primary null hypothesis to be tested is that the mean for the primary efficacy variable for VNZ/TEZ/D-IVA is inferior by >3 percentage points compared to ELX/TEZ/IVA. The primary analysis of the primary estimand will be performed using a mixed-effects model for repeated measures (MMRM) with change from baseline at Day 15, Week 4, Week 8, Week 16, and Week 24 as the dependent variable. The model will include fixed categorical effects for treatment, visit, age at screening (<18 versus ≥18 years of age), and treatment-by-visit interaction, with baseline ppFEV₁ and baseline SwCl as continuous covariates. The model will be estimated using restricted maximum likelihood. Denominator degrees of freedom for the *F*-test for fixed effects will be estimated using the Kenward-Roger approximation⁵. An unstructured covariance structure will be used to model the within-subject errors. If the model estimation does not converge, an alternative covariance structure like compound symmetry will be used. Conditional on the observed data and covariates, missing data will be assumed to be missing at random (MAR).

The primary result obtained from the model will be the estimated treatment difference through Week 24 (estimated by averaging Weeks 16 and 24). The adjusted mean with a 2-sided 95% CI and the 1-sided *P* value for non-inferiority will be provided. The primary null hypothesis will be rejected, and non-inferiority demonstrated, if the lower bound of the CI is ≥-3.0.

The primary null hypothesis of non-inferiority described above will be tested based on the FAS.

If non-inferiority for the primary endpoint is demonstrated, and if the lower bound of the same 95% CI is greater than 0, then superiority for the primary endpoint is also demonstrated, and the 2-sided *P* value for superiority will be presented.

The estimated within-group change from baseline and treatment difference at each post-baseline visit, obtained from the model, will be provided. The estimated within-group change and its standard error (SE) at each post-baseline visit will also be plotted by treatment group.

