8.3.2.3 Multiplicity Adjustment

A hierarchical testing procedure will be used to control the overall type I error at an alpha of 0.05. The key secondary endpoints will be formally tested at an alpha level of 0.05 only if the primary analysis of absolute change from baseline in ppFEV₁ through Week 24 is statistically significant, i.e., if the null hypothesis of inferiority has been rejected. For a test at any step to be considered statistically significant within the testing hierarchy, it must be statistically significant, and all previous tests (if any) within the hierarchy must be statistically significant at the 0.05 level (one-sided 0.025 level for the primary endpoint). The testing order of the key secondary endpoints is as follows:

- Absolute change from baseline in SwCl through Week 24
- Proportion of subjects with SwCl <60 mmol/L through Week 24 (pooled with data from Study 103)
- Proportion of subjects with SwCl <30 mmol/L through Week 24 (pooled with data from Study 103)

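### The two alpha-controlled pooled responder tests (SwCl <60 and <30 mmol/L) use an available-data GEE that needs a stronger missing-data assumption than the SwCl MMRM one step earlier, with no sensitivity analysis; the likely bias is small and the repair is cheap.

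*SAP*

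**What the plan says.** SAP 8.3.2.3 sets a fixed sequence: "A hierarchical testing procedure will be used to control the overall type I error at an alpha of 0.05". After the primary ppFEV1 test the order is continuous SwCl change, then the pooled proportion with SwCl <60 mmol/L, then the pooled proportion with SwCl <30 mmol/L.

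For continuous SwCl, SAP 8.3.2.2 says: "The analysis of absolute change from baseline in SwCl through Week 24 will be based on an MMRM similar to the primary analysis". That primary model (SAP 8.3.1.3) carries an explicit statement: "Conditional on the observed data and covariates, missing data will be assumed to be missing at random (MAR").

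For the <60 endpoint, SAP 8.3.2.2 says the response at each visit "will be analyzed using a generalized estimating equations (GEE) model". The terms are treatment, visit, their interaction, age group, genotype group, baseline ppFEV1 and "baseline SwCl as continuous covariates". It adds: "A logit link function and an unstructured working correlation matrix will be used in the GEE model". If convergence still fails after genotype is simplified or removed, "an alternative covariance structure like compound symmetry will be used". For <30: "The estimand and analysis will be similar to that for the pooled analysis of proportion of subjects with SwCl <60 mmol/L through Week 24".

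No weighting, imputation, non-response rule, missing-data assumption or missing-data sensitivity analysis is given for either responder endpoint. SAP 8.1 leaves missing data to later sections where relevant, and none takes it up for the GEE. The only alternative estimand (SAP 8.3.1.4 and Appendix D) is for ppFEV1. SAP 8.3.2.1 also sets SwCl results to missing when the sweat volume is below 15 µL or the value exceeds 160 mmol/L.

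**The concern.** A likelihood-based MMRM uses each subject's observed SwCl to allow for what is missing later, so it remains valid if dropout depends on those observed values. A GEE on available binary responses does not do this in general. It allows for missingness explained by its covariates, which include baseline SwCl. It does not generally allow for missingness that depends further on Day 15, Week 4 or Week 16 SwCl. It also reduces those readings to above or below a threshold.

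Intercurrent events are handled by treatment policy, using values after discontinuation where they exist. Subjects without a Week 16 or Week 24 value will often have earlier on-treatment SwCl on record. If the reasons for missing data differ between arms, the odds ratio averaged over Weeks 16 and 24 can be biased either way, in two tests that share the trial's controlled error rate.

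The 160 mmol/L rule adds a small point of its own. Taken at face value, such a reading is a non-response at both thresholds, so setting it to missing is missingness by outcome.

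**Working it through.** **1. The plan's own figures.** SAP 6.2.2 gives SD 14 mmol/L, difference 5 mmol/L, 200 per arm, 10% dropout, two-sided 0.05. With n = 200 × 0.9 = 180 per arm, SE = 14 × √(2/180) = 1.476. Power ≈ Φ(5/1.476 − 1.960) = Φ(1.428) = 92.3% (92.2% by noncentral t). The stated figure of more than 90% reproduces. No power or dropout figure is given for the responder endpoints, so this point changes no stated number.

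**2. The two assumptions side by side.**
- SwCl MMRM: missingness may depend on covariates and on observed SwCl at any visit.
- Responder GEE: missingness may depend on covariates (baseline SwCl, baseline ppFEV1, age group, genotype group), but in general not further on post-baseline SwCl.

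The second is a special case of the first. Where the GEE's condition holds, the MMRM's holds too; the converse fails.

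**3. Simulation of the SAP's model.** A logit GEE was fitted with unstructured working correlation, treatment by visit and baseline SwCl, averaging Weeks 16 and 24 on the log-odds scale.
- From the SAP: SD 14, difference 5 or 0, 10% dropout.
- Assumed: baseline SwCl mean 45 and SD 20; subject SD 11 and residual SD 8.66 (11² + 8.66² = 196 = 14²); dropout before Weeks 16 and 24 at about 5% each (1 − 0.95² = 9.75%), driven by the previous visit's change at log-odds 1 per 14 mmol/L.
- Benchmarks: complete data, and a GEE weighted by the inverse of the true simulated probabilities of remaining observed.

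| Missingness, difference 5 | <60 complete | <60 GEE | <60 weighted | <30 complete | <30 GEE | <30 weighted |
|---|---|---|---|---|---|---|
| Completely at random | 1.88 | 1.89 | 1.89 | – | – | – |
| MAR, same in both arms | 1.88 | 1.88 | 1.89 | 1.87 | 1.86 | 1.88 |
| MAR, control arm only | 1.88 | 1.83 | 1.89 | 1.87 | 1.83 | 1.87 |
| MAR, opposite by arm | 1.88 | 1.98 | 1.88 | 1.87 | 1.96 | 1.89 |

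A separate run with the unstructured correlation, with poor responders dropping out in the new-drug arm only, moved the OR from 1.78 to 1.86 (log ratio 0.044).

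**4. Bias in standard errors and test size.** Shift s = bias / SE; two-sided error = Φ(−1.960 + s) + Φ(−1.960 − s). The documents do not give the size of Study 103, so pooled N is varied.

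| No effect, opposite mechanisms | Bias in log OR | N = 400 | N = 800 | N = 1000 |
|---|---|---|---|---|
| <60, SE | 0.0419 | 0.262 | 0.185 | 0.166 |
| <60, shift | | 0.16 | 0.23 | 0.25 |
| <60, two-sided error | | 0.053 | 0.056 | 0.057 |
| <30, SE | 0.0438 | 0.260 | 0.184 | 0.165 |
| <30, shift | | 0.17 | 0.24 | 0.27 |
| <30, two-sided error | | 0.053 | 0.057 | 0.058 |

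With the same mechanism in both arms the <60 error stays at 0.050. For <30 with the control-arm-only mechanism (difference 5), the bias is −0.0246, or 0.10 to 0.15 SE (SE 0.256 to 0.162).

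**5. Monte Carlo error.** The <60 row above is one sample of 50,000. The mean of four samples of 60,000 gave 0.0546 for the same null case. That would be 0.0546/0.262 = 0.21 to 0.0546/0.166 = 0.33 SE, with two-sided error 0.055 to 0.063. In that larger run the completely-at-random null case showed an apparent bias of 0.0055 where none should exist, so the third decimal carries no weight.

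**6. The fallback and the repair.** A separate simulation with exchangeable working correlation, the form of the named fallback, gave OR 1.84 on complete data. With drivers differing by arm the available-data GEE gave 1.91; imputing continuous SwCl first gave 1.81. Its Monte Carlo error is a few hundredths, so this is indicative only.

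**The case against.** The strongest reply is that the analysis is pre-specified and the exposure is limited. Subjects who stop treatment are asked to attend all later visits (Protocol 9.1.5.2), sweat chloride is taken at the early-termination visit (Protocol Table 3-2), and the analysis windows are wide (days 71 to 141 for Week 16, 141 to 211 for Week 24). Baseline SwCl is already a covariate, and the unstructured correlation absorbs much of the remaining dependence. The inflated error needs dropout that differs by arm, for which the documents give no evidence; the control-arm-only case lowered the odds ratio. All of this stands and sets the weight of the point. It does not supply the missing assumption or a sensitivity analysis.

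Stronger readings are tempting and should be resisted:
- A reader might infer that the two models rest on incompatible assumptions. They are nested: one is stronger.
- A reader might say both models use the same data. The MMRM uses the Study 102 full analysis set and the GEE adds Study 103, so this is exact only for the Study 102 part. The MAR sentence is written for ppFEV1 and reaches SwCl through the reference to a similar model.
- A reader might quote a one-sided error of about 0.04 against 0.025. The tests are two-sided: at a shift of 0.2 SE the other tail falls to about 0.015, and the total is about 0.055.
- A reader might cite the larger distortion under an independence working correlation (OR 2.20 against 1.88 with opposite mechanisms). The SAP does not name that structure.

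**Conclusion.** The point holds as a gap in assumption and sensitivity analysis. As written, the two confirmatory responder tests are generally valid only if missingness, given the model covariates, does not depend on post-baseline SwCl. That is a stronger condition than the MAR assumption behind the preceding SwCl test, although the earlier values are on file.

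At the planned 10% dropout the bias is near zero when the mechanism is common to both arms. When it differs by arm, the bias is about 0.1 to 0.25 SE in either direction; one larger run would put it at 0.33 SE at a pooled N of 1000. The adverse opposite-direction case gives a two-sided error of about 0.053 to 0.058, or just over 0.06 on that run. These sizes rest on assumed pooled N, baseline distribution, correlations and dropout mechanisms. That no weighting is used is inferred from the SAP's silence.

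The documents do not support a claim that the responder results would be unreliable or that type I error control fails materially. This is a cheap improvement.

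**What to change.** State the missing-data assumption for the responder endpoints in SAP 8.3.2.2, and add the following:

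1. Multiply impute continuous SwCl within treatment arm under MAR, using baseline SwCl, all earlier post-baseline SwCl, baseline ppFEV1, age group and genotype group.
2. Apply the 10 mmol/L floor of SAP 8.3.2.1 after imputation. It changes neither response, since 10 lies below both thresholds, but keeps imputed and observed values on one rule.
3. Dichotomise at 60 and 30 mmol/L.
4. Fit the planned GEE to each imputed data set and combine the log odds ratios by Rubin's rules.
5. Count values reported above 160 mmol/L as non-responses in the responder endpoints, or check the effect of leaving them missing.

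If the sponsor keeps the available-data GEE as the test, pre-specify steps 1 to 5 as its sensitivity analysis. SAP section 3 requires revisions to be approved before database lock, so the change must be made by then. This aligns the responder analysis with the MMRM's assumption; it does not test departures from MAR.

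The cost is extra programming and a stated seed and number of imputations. No new data are needed, and the estimand, model terms and testing order stay as they are.

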8.3.2.3 Multiplicity Adjustment

A hierarchical testing procedure will be used to control the overall type I error at an alpha of 0.05. The key secondary endpoints will be formally tested at an alpha level of 0.05 only if the primary analysis of absolute change from baseline in ppFEV₁ through Week 24 is statistically significant, i.e., if the null hypothesis of inferiority has been rejected. For a test at any step to be considered statistically significant within the testing hierarchy, it must be statistically significant, and all previous tests (if any) within the hierarchy must be statistically significant at the 0.05 level (one-sided 0.025 level for the primary endpoint). The testing order of the key secondary endpoints is as follows:

- Absolute change from baseline in SwCl through Week 24
- Proportion of subjects with SwCl <60 mmol/L through Week 24 (pooled with data from Study 103)
- Proportion of subjects with SwCl <30 mmol/L through Week 24 (pooled with data from Study 103)

8.3.3 Analysis of Other Secondary Variables

8.3.3.1 Definition of Variables

Pulmonary exacerbation (PEX): A PEX is defined as a new or change in antibiotic therapy (IV, inhaled, or oral) for any 4 or more of the following signs/symptoms:

- Change in sputum
- New or increased hemoptysis
- Increased cough
- Increased dyspnea
- Malaise, fatigue, or lethargy
- Temperature above 38°C (equivalent to approximately 100.4°F)
- Anorexia or weight loss
- Sinus pain or tenderness

- Change in sinus discharge
- Change in physical examination (PE) of the chest
- Decrease in pulmonary function by 10%
- Radiographic changes indicative of pulmonary infection

The number of PEx through Week 52 is defined as the total number of PEx during the PEx analysis period (defined in 8.1).

Cystic Fibrosis Questionnaire – Revised (CFQ-R): The CFQ-R^{6,7,8} is a validated CF-specific instrument that measures quality-of-life domains. This study utilizes three different versions of CFQ-R:

- CFQ-R for Children Ages 12 and 13 (subjects 13 years and younger on the date of informed consent)
- CFQ-R for Adolescents and Adults (subjects 14 years and older on the date of informed consent)
- CFQ-R for Parents/Caregivers (subjects 13 years and younger on the date of informed consent)

In all three versions, specific questions belonging to a domain are scored 1, 2, 3, or 4. The CFQ-R domain score, e.g., physical domain score or respiratory domain score, is defined as a scaled score as follows:

Scaled score for a domain = $100 \times (\text{mean (scores of all questions in the domain)} - 1)/3$, where the score from a negatively phrased question is first reversed, i.e., reversed score = $5 - \text{actual score}$, so that 1 always represents the worst condition and 4 the best condition. The (scaled) domain score ranges from 0 (worst condition) to 100 (best condition). The scaled score for a specific domain will not be calculated if more than half of the questions in the domain have missing scores.

The (scaled) domain score from the CFQ-R for Children Ages 12 and 13 and for Adolescents and Adults will be pooled for analysis purposes.

8.3.3.2 Analysis Method

Number of PEx through Week 52: The number of PEx through Week 52 will be analyzed, and the estimated PEx rate (per year, with 48 weeks as 1 year) will be presented. The difference in PEx rate and the associated 95% CI will also be provided.

Absolute change from baseline in CFQ-R Respiratory Domain (RD) score through Week 24: The analysis of absolute change from baseline in CFQ-R RD score through Week 24 will be based on an MMRM similar to the primary analysis of the primary estimand (8.3.1.3), with absolute change from baseline in CFQ-R RD score at Week 8, Week 16, and Week 24 as the dependent variable. The estimated treatment difference through Week 24 (estimated by averaging Weeks 16 and 24) will be presented along with the 2-sided 95% CI. The estimated within group change from baseline and treatment difference at each post-baseline visit, obtained from the model, will be provided.

Absolute change from baseline in ppFEV₁ through Week 52: Analysis of this endpoint will be based on an MMRM similar to the primary analysis of the primary estimand (8.3.1.3), with the addition of data from Week 36 and Week 52. The estimated change through Week 52 will be based on averaging estimates from Weeks 16, 24, 36 and 52. The post-baseline raw values and the absolute change from baseline at each post-baseline visit through Week 52 will be summarized descriptively (n, mean, SD, median, min, max).

Absolute change from baseline in SwCl through Week 52: Analysis of this endpoint will be based on an MMRM similar to that for absolute change from baseline in SwCl through Week 24 (8.3.2.2), with the addition of data from Week 36 and Week 52. The estimated change through Week 52 will be based on averaging estimates from Weeks 16, 24, 36 and 52. The post-baseline raw values and the absolute change from baseline at each post-baseline visit through Week 52 will be summarized descriptively (n, mean, SD, median, min, max).

Proportion of subjects with SwCl <60 mmol/L through Week 24 (within-study): Analysis of this endpoint will be based on a GEE model similar to that for the proportion of subjects with SwCl <60 through Week 24 using the PFAS (8.3.2.2), but instead will be based on the FAS. Genotype group will not be included in the model since all subjects in Study 102 will be F/MF.

Proportion of subjects with SwCl <30 mmol/L through Week 24 (within-study): Analysis of this endpoint will be based on a GEE model similar to that for the proportion of subjects with SwCl <30 through Week 24 using the PFAS (8.3.2.2), but instead will be based on the FAS. Genotype group will not be included in the model since all subjects in Study 102 will be F/MF.

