8 STATISTICAL ANALYSIS

8.1 General Considerations

The Schedule of Assessments is provided in the CSP for Study 102. The precision standards for reporting safety and efficacy variables are provided in an internal Biometrics document that specifies the programming rules including the precision for derived variables.

Continuous variables will be summarized using the following descriptive summary statistics: the number of subjects (n), mean, SD, median, minimum value (min), and maximum value (max).

Categorical variables will be summarized using counts and percentages. Percentages will be presented to 1 decimal place.

Baseline value:

For all safety endpoints:

- Unless otherwise specified, baseline will be defined as the most recent non-missing measurement (scheduled or unscheduled) collected before the first dose of study drug in the Treatment Period (i.e., the Day 1 Visit).

For all efficacy endpoints:

- Except for SwCl, baseline will be defined as the pre-dose Day 1 value. If the pre-dose Day 1 value is missing, the most recent pre-dose, non-missing value on or after the Day -14 visit, including unscheduled visits, will be used as baseline.
- For SwCl, baseline will be defined as the average of the two most recent pre-dose, non-missing values on or after the Day -14 visit, including unscheduled visits. If only 1 non-missing value is available during this interval, the available value will be considered as baseline.

Absolute change from baseline will be calculated as post-baseline value - baseline value.

Relative change from baseline will be calculated as (post-baseline value - baseline value)/baseline value.

The **Treatment-emergent (TE) Period for the Run-in Period** will be from the first dose date of study drug in the Run-in Period to (1) the first dose date of study drug in the Treatment Period for subjects who complete the Run-in Period and continue to the Treatment Period, or (2) 28 days after the last dose date of study drug in the Run-in Period or to the completion of study participation date, whichever occurs first, for subjects who do not continue to the Treatment Period (e.g., subjects who do not meet the conditions to enter the Treatment Period).

The **TE Period for the Treatment Period** will be from the first dose date of study drug in the Treatment Period (VNZ/TEZ/D-IVA or ELX/TEZ/IVA) to 28 days after the last dose date of study drug in the Treatment Period or to the completion of study participation date, whichever occurs first.

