8.3.4.2 Analysis Method

Proportion of subjects with SwCl <60 mmol/L through Week 52 (within-study): Analysis of this endpoint will be based on a GEE model similar to that for the proportion of subjects with SwCl <60 through Week 24 using the FAS (8.3.3.2), with the addition of data from Week 36 and Week 52.

Proportion of subjects with SwCl <30 mmol/L through Week 52 (within-study): Analysis of this endpoint will be based on a GEE model similar to that for the proportion of subjects with SwCl <30 through Week 24 using the FAS (8.3.3.2), with the addition of data from Week 36 and Week 52.

Absolute change from baseline in BMI at Week 52: Analysis of this variable will be based on an MMRM similar to the primary analysis of the primary estimand (8.3.1.3). Data obtained from Day 15, Week 4, Week 8, Week 16, Week 24, Week 36, and Week 52 will be included in the

model. The estimated treatment difference at Week 52 will be presented along with the 2-sided 95% CI. The post-baseline raw values and the absolute change from baseline at each post-baseline visit through Week 52 will be summarized descriptively (n, mean, SD, median, min, max), in addition.

Absolute change from baseline in BMI z-score at Week 52 (for subjects ≤ 20 years of age at Baseline): Analysis of this variable will be based on an MMRM similar to the primary analysis of the primary estimand (8.3.1.3), excluding the term age at screening (< 18 versus ≥ 18 years of age), for subjects ≤ 20 years of age at Baseline. Data obtained from Day 15, Week 4, Week 8, Week 16, Week 24, Week 36, and Week 52 will be included in the model. The estimated treatment difference at Week 52 will be presented along with the 2-sided 95% CI. The post-baseline raw values and the absolute change from baseline at each post-baseline visit through Week 52 will be summarized descriptively (n, mean, SD, median, min, max), in addition.

Absolute change from baseline in weight at Week 52: Analysis of this variable will be based on an MMRM similar to the primary analysis of the primary estimand (8.3.1.3). Data obtained from Day 15, Week 4, Week 8, Week 16, Week 24, Week 36, and Week 52 will be included in the model. The estimated treatment difference at Week 52 will be presented along with the 2-sided 95% CI. The post-baseline raw values and the absolute change from baseline at each post-baseline visit through Week 52 will be summarized descriptively (n, mean, SD, median, min, max), in addition.

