Absolute change from baseline in CFQ-R RD score through Week 52: Analysis of this domain will be based on an MMRM similar to that for absolute change from baseline in CFQ-R RD score through Week 24 (8.3.3.2), with the addition of data from Week 52. The estimated change through Week 52 will be based on averaging estimates from Weeks 16, 24, and 52. The estimated treatment difference through Week 52 will be presented along with the 2-sided 95% CI. The post-baseline raw values and the absolute change from baseline at each post-baseline visit through Week 52 will be summarized descriptively (n, mean, SD, median, min, max), in addition.

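### The SAP names no own-baseline covariate for the CFQ-R RD, BMI, BMI z-score and weight models; read as written, this costs precision, mainly for CFQ-R RD

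*SAP*

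**What the plan says.** The primary MMRM in SAP 8.3.1.3 lists its terms by name: treatment, visit, treatment-by-visit, age group, and baseline ppFEV1 "and baseline SwCl as continuous covariates". It has no generic term for the baseline of whatever endpoint is being modelled.

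Other endpoints reuse that model by reference:

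- **CFQ-R RD through Week 24 (8.3.3.2):** the analysis of change in "CFQ-R RD score through Week 24 will be based on an MMRM similar to the primary analysis of the primary estimand". Only the response and the visits (Weeks 8, 16 and 24) are changed. The result is a treatment difference "estimated by averaging Weeks 16 and 24) will be presented along with the 2-sided 95% CI".
- **CFQ-R RD through Week 52 (8.3.4.2):** built on the Week 24 CFQ-R model with Week 52 added. "The estimated change through Week 52 will be based on averaging estimates from Weeks 16, 24, and 52".
- **BMI, BMI z-score and weight at Week 52 (8.3.4.2):** the weight entry is typical: "Absolute change from baseline in weight at Week 52: Analysis of this variable will be based on an MMRM similar to the primary analysis". For BMI z-score the one stated change of terms is "excluding the term age at screening".

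Protocol 12.3.3.2 and 12.3.3.4 leave the details of these analyses to the SAP. SAP 8.1 does define the baseline for every efficacy endpoint other than SwCl: "baseline will be defined as the pre-dose Day 1 value", with a fallback if that value is missing.

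**The concern.** For ppFEV1 and SwCl the endpoint's own baseline is in the model, because both are named covariates. When the same list is carried to CFQ-R RD, BMI, BMI z-score or weight, the strongest usual predictor of change drops out unless someone adds it. Where the SAP alters the terms of a borrowed model it tends to say so. The age term "will be removed from the MMRM" in the age subgroups and is excluded for BMI z-score, and genotype group is dropped from the within-study GEE models. Silence about the own baseline therefore reads most naturally as no change to the covariates.

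The stake is precision and reproducibility. CFQ-R RD is a patient-reported other secondary endpoint whose planned result is an estimate with a CI, so interval width is much of what is reported. Two programmers could also read the text differently and report different intervals.

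**Working it through.** **Plan's own figures.** The documents give no SD, correlation or power for these four endpoints. The stated power figures serve only to fix the evaluable n: 200 per arm less 10% drop-out is 180 (SAP 6.2.1).

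- Primary: 3 / (8 × √(2/180)) = 3.558; less 1.96 is 1.598, so power is 94.5%.
- SwCl: 5 / (14 × √(2/180)) = 3.388; less 1.96 is 1.428, so power is 92.3%.

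Both agree with the stated figure of more than 90%.

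**Assumptions.** Equal variance s² at all visits, and a common correlation r between baseline and follow-up visits and among follow-up visits. The contrast is the mean of k follow-up visits minus baseline.

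- Without own baseline: V0 = s²[(1+(k−1)r)/k + 1 − 2r]
- With own baseline: V1 = s²[(1+(k−1)r)/k − r²]
- Ratio: V1/V0 = (1+kr)/(1+k), which is below 1 for every r < 1. The CI narrows by 1 − √(V1/V0).

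**CFQ-R RD**

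| r | Week 24 (k = 2): ratio, CI narrower by | Week 52 (k = 3): ratio, CI narrower by |
|---|---|---|
| 0.5 | 0.667, 18.4% | 0.625, 20.9% |
| 0.6 | 0.733, 14.4% | 0.700, 16.3% |
| 0.7 | 0.800, 10.6% | 0.775, 12.0% |
| 0.8 | 0.867, 6.9% | 0.850, 7.8% |

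**Overlap with the covariates already present.** Suppose ppFEV1 and SwCl explain a share q² of baseline CFQ-R variance and act on follow-up only through it. For k = 2, V0 becomes s²[1.5(1−r) − (1−r)²q²] and V1 is unchanged. With q² = 0.20 and r = 0.6: V0 = 0.600 − 0.032 = 0.568, V1 = 0.440, ratio 0.775, CI 12.0% narrower. At r = 0.5, 0.7 and 0.8 the gain is 15.5%, 8.7% and 5.6%.

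**On the score scale** (k = 2, r = 0.6, 180 per arm, no overlap). Half-width = 1.96 × SD × √(V × 2/180), where V is V0 or V1 in units of s².

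- SD 15: 2.40 points without own baseline (V = 0.60), 2.06 with it (V = 0.44).
- SD 20: 3.20 against 2.74.
- Equivalent sample size: 360 × 0.733 = 264 subjects with the covariate match 360 without it. With the 20% overlap this becomes 360 × 0.775 = 279.

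**Body size at Week 52** (k = 1, ratio (1+r)/2). At r = 0.90, 0.95 and 0.98 the ratio is 0.950, 0.975 and 0.990, so the CI narrows by 2.5%, 1.3% and 0.5%.

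**Checks.** A simulation (180 per arm, SD 18, no true difference, one covariate correlated 0.3 with baseline, 3,000 runs) gave SEs of 1.453 without and 1.260 with own baseline at r = 0.6 (13.2% narrower), and 1.263 and 1.142 at r = 0.7 (9.6%). The formula with q² = 0.3² = 0.09 gives 13.3% at r = 0.6. Mean estimates were within 0.04 points of zero in both models. A separate calculation let the follow-up correlation differ from r and put baseline ppFEV1 in both models, with r from 0.5 to 0.7. The Week 16/24 CI was 9.8% to 23.4% wider without own baseline.

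**Chance imbalance.** Without own baseline, a baseline difference of one standard error moves the CFQ-R estimate by about (1−r) × SD × √(2/180). That is 0.5 points (SD 15, r = 0.7) to 1.1 points (SD 20, r = 0.5).

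**The case against.** The SAP calls these models similar to the primary one, not identical. In the primary model baseline ppFEV1 is the endpoint's own baseline, so carrying the model over could mean carrying over that role. The age-subgroup precedent is weak, because there the SAP says the same model is applied. The remaining precedents are removals of terms and do not show how an added baseline would be handled. This stands in part: the text is under-specified, and omission is the more natural reading but not the only one.

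The size of the loss rests on assumed correlations. After a stabilizing run-in on ELX/TEZ/IVA, with one arm staying on it, r might exceed 0.8. The same formula gives a Week 24 gain of 5.1% at r = 0.85 and 3.4% at r = 0.90. CFQ-R numbers may also fall below 180 per arm, since Protocol 11.5.3 exempts subjects without a validated translation. That would change the half-widths but not the ratios.

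Finally, these endpoints are supportive, no power is claimed for them, and the body-size gain is negligible. That limits the priority of the point. It does not give a reason to leave the covariate out.

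**Conclusion.** The concern holds. No passage names an own-baseline covariate for CFQ-R RD (through Week 24 or Week 52), BMI, BMI z-score or weight. Under equal variances and a common correlation, the direction of the loss does not depend on the value assumed for r, but its size does. For r of 0.5 to 0.8, the CFQ-R RD interval through Week 24 could be about 6% to 18% narrower, counting the overlap case. The cost falls mainly on CFQ-R RD as long as its correlation with baseline is lower than that of body size.

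There is no bias under randomization and no effect on type I error. All four endpoints are outside the hierarchy in SAP 8.3.2.3. This is a recommended improvement, not a flaw that threatens the trial's conclusions.

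**What to change.** Before database lock, amend SAP 8.3.3.2 and 8.3.4.2 to state:

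> The MMRMs for CFQ-R RD (through Week 24 and through Week 52), BMI, BMI z-score and weight each include the continuous baseline value of their own endpoint, in addition to baseline ppFEV1, baseline SwCl and, except for BMI z-score, age at screening (<18 versus ≥18 years).

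This also settles whether the own baseline is added to ppFEV1 and SwCl or replaces them. Replacing ppFEV1 would be a possible alternative, but adding keeps the models closest to the primary one.

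The cost is one sentence and one covariate per model. The baselines are already collected and defined (SAP 8.1), baseline CFQ-R RD is already summarized (SAP 8.2.2), and SAP section 3 provides for amendments before the lock.
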